3.2. Challenge Phase

Four weeks after completion of the two-dose vaccination schedule (approximately 28 days after Visit 3) subjects will be admitted the day before the challenge date (Day 56) and will stay for 9 days in the inpatient unit. Biological sample collection could start for logistical reason at Day 56 (the day of admission before challenge). The day of challenge (Visit 5; Day 57), they will be administered a 1500 CFU challenge dose of *S. sonnei* 53G. Before receiving the challenge, all inclusion and exclusion criteria and hematology will be assessed.

When assessing inclusion and exclusion criteria, the investigator will also inquire about antibiotic treatment during the week prior to the challenge date. Any subject who had a course of antibiotic the week prior to challenge, will not receive the challenge agent.

Subjects will fast for 90 minutes prior to receiving the *S. sonnei* 53G challenge inoculum and an additional 90 minutes after challenge. All subjects in the same cohort will be challenged in the same day using the same inoculum, which will ensure the consistency of the dose used. Approximately 5 minutes before drinking the challenge suspension, the subject will drink a 120 mL solution of sodium bicarbonate to neutralize gastric acidity. A subject with fever or signs of acute illness will not receive the challenge agent and any subject who vomits following ingestion of the challenge agent will not be re-dosed. A note will be made in the subject source documents regarding the apparent amount of the vomitus (small, moderate or large). The subject will still continue in the study and undergo all study-related procedures. Care will be taken to ensure that a minimum amount of time, not to exceed 2 hours, is spent between the reconstitution of the challenge inoculum and the oral administration of the inoculum to the subject.

Two mL of the inoculum will be retained for pre- and post-challenge quantification of the dose. Aliquots of the retained inoculum will be streaked onto trypticase soy agar (TSA) plates and after incubation, average number of colonies on the TSA plates will be counted and CFU/mL will be calculated. Study staff will take all necessary precaution needed for handling of *S. sonnei* 53G and adhere to the CCHMC policy and procedures.

During the first 8 days in the inpatient unit (Day 57 to Day 64) following challenge, subjects will be monitored daily for AEs, gastrointestinal or other systemic signs and symptoms. Subjects will be assessed for vital signs (including sitting blood pressure, temperature and pulse rate) according to local standards for inpatient care. Stool analysis will be carried out daily during the inpatient stay. All stools will be collected and visually assessed for consistency, blood or mucus. Stools that are loose or watery (grades 3-5) will be weighed, and if there is visible blood, a Hemoccult test will be performed to confirm presence of occult blood. Up to two stools with blood present by visual inspection in a 24 hour period will be tested by Hemoccult. Study staff will record the information in the subject's source document. If a subject is unable to produce a stool by midnight, a rectal swab will be obtained (up to 2 adequately collected swabs per day). Study staff will record the information in the subject's source document. The first stool sample collected during a 24 hour period on the day after challenge agent administration (from 00:01 to 24:00) will be analyzed by culture and quantitative polymerase chain reaction (qPCR) specific for S. sonnei 53G. The day before discharge (Day 64), two stool samples will be collected to confirm that the subject is no longer shedding. Instructions for appropriate

205626 (S SONNEI MONO GMMA SBVGH-003 [H03_03TP])
Protocol Amendment 6 Final

collection, transportation and storage of stool samples will be provided to the investigators. For diarrhea episodes to be considered as separate episodes, there should be at least a 6-hour interval between them (refer to Section 4 for details on stool grading).

On the 5th day after challenge (Day 62), subjects will receive as first-line treatment 500 mg of ciprofloxacin twice daily for 3 days. Subjects with contraindication to ciprofloxacin may receive as second-line treatment trimethoprim-sulfamethoxazole (160 mg/800 mg twice daily), amoxicillin (500 mg three times daily) for 5 days, or any antibiotic that is deemed suitable according to local guidelines and the investigator's assessment can be used.

Subjects may be treated with antibiotics before the 5th day after challenge (Day 62) if:

- They have diarrhea (any severity stool Grade 3 or higher) and two or more of the following symptoms: severe abdominal pain/cramps, severe nausea, severe headache, severe myalgia, severe arthralgia, gross blood in ≥ 2 stools, any fever (≥ 38.0°C measured orally), or any vomiting.
- They experience unexpectedly severe events such as hypotension (disproportionate to volume loss), renal dysfunction, or altered mental state (e.g. somnolence) at the discretion of the investigators.
- A study physician determines early treatment is warranted for other reasons.

A subject receiving early antibiotic treatment will still remain on the unit until the planned day of discharge (the 9th day of inpatient stay: Day 65). On that day, if a subject is clinically well and has had at least 2 negative stool cultures, collected at least 6 hours apart, for *S. sonnei*, s/he will be discharged. A subject that, on the planned day of discharge, still had S. *sonnei* isolated from the Day 64 stools will be asked to remain in the unit until s/he is no longer shedding. A subject still shedding 48 hours after initiation of ciprofloxacin will be switched to a Septra DS (1 tablet twice a day for five days). If a subject is still positive 48 hours after the second-line antibiotic is administered, a culture and antibiotic sensitivity test will be obtained and therapy initiated based on sensitivity results. If a subject has two consecutive negative stool samples and is eligible to be discharged from the inpatient stay but did not finish his treatment course, s/he can be given the remaining doses to complete at home.

Following discharge, subjects will return at 28 days (Visit 6), 56 days (Visit 7) and 6 months (Visit 8) after challenge for outpatient clinical assessment. During these visits, clinical assessment will be done to assess their general health status and find out about the occurrence of AESI, any AE and SAE.

[figure not shown]
Subjects will be advised at the time of their discharge to contact the study staff/doctor if they feel unwell. The subjects will be followed up until 6 months after the challenge. At the last study visit, at 6 months after challenge, the subject will be reviewed for the occurrence of any AESI and the site staff will ensure all AEs are resolved.

Through the entire study, all subjects will be advised to report to the study facility whenever they are sick. Standard patient care, according to local guidelines will be provided for all illnesses in both the outpatient and inpatient facilities. Additional investigations may be conducted if the investigator considers them necessary to better evaluate the subject's condition. An overview of the study design is given in Figure 1.

205626 (S SONNEI MONO GMMA SBVGH-003 [H03_03TP])

Protocol Amendment 6 Final

Figure 1 Study design (Amended: 23 July 2019)

*Refer to Section 3.2 for details of procedures during the inpatient stay (Amended: 23 July 2019)

Scr: Screening

N: Number of subjects

B: Blood sampling

S: Stool sampling

U: Urine sampling

205626 (S SONNEI MONO GMMA SBVGH-003 [H03_03TP]) Protocol Amendment 6 Final

Protocol waivers or exemptions are not allowed unless necessary for the management of immediate safety concerns. Therefore, adherence to the study design requirements, including those specified in the outline of study procedures (Section 6.4.1), are essential and required for study conduct.

- **Experimental design:** Phase IIB, observer-blind, randomized, placebo control, mono-centric study with two parallel groups (*S. sonnei* group and placebo group).
- **Duration of the study**: Each subject will be followed up for approximately 6 months after challenge with the pathogenic *S. sonnei* strain 53G, with a total study duration of approximately 32 weeks (i.e., 8 months) for each study subject.
 - Epoch 001: Starting at Screening Visit (Day -45 to Day -1) and ending before Visit 1 (Day 1).
 - Epoch 002: Starting the day of randomization and first vaccination (Visit 1) and ending before the receipt of the challenge agent, 28 days after second vaccination (Visit 5).
 - Epoch 003: Starting with the receipt of the challenge agent at 28 days after second vaccination (Visit 5) and ending 6 months after challenge (Visit 8).
- Primary completion date (PCD): End of inpatient stay (Visit 5, Day 64). (Amended: 23 July 2019)

Refer to glossary of terms for the definition of PCD.

• End of Study (EoS): Last testing results released of samples collected for primary and secondary objectives at Visit 8.

Refer to glossary of terms for the definition of EoS.

• Study groups:

Table 1 Study groups and epochs foreseen in the study

Chudu	Number of	Epochs						
Study	Number of subjects	Age (Min - Max)	Epoch 001	Epoch 002	Epoch 003			
groups	Subjects		Screening	1st and 2nd vaccination	Challenge			
S. sonnei	36	18 years – 50 years	Х	х	Х			
Placebo	36	18 years – 50 years	Х	х	Х			

Table 2 Study groups and treatment foreseen in the study

Treatment name	Vaccine/ placebo/	Study Groups					
Treatment name	challenge agent name	S. sonnei	Placebo				
S. sonnei	1790GAHB	X					
Placebo	GAHB-Placebo		Х				
Challenge	S. sonnei 53G strain	Х	Х				

• **Control:** Placebo control with GAHB-Placebo with the same composition as the vaccine except the active ingredient. GAHB-Placebo will also be used as diluent for bedside mixing of the vaccine.

205626 (S SONNEI MONO GMMA SBVGH-003 [H03_03TP])
Protocol Amendment 6 Final

- Vaccination schedule: Subjects will receive 2 doses of either the study vaccine or placebo 28 days apart. At 28 days after the second dose, all subjects will receive the challenge dose.
- **Treatment allocation**: Following the screening period before the first vaccination (Day -45 to Day -1), subjects will be randomized in a 1:1 ratio to receive either the study vaccine or the placebo.
- **Blinding**: The study will be observer-blind.

Table 3 Blinding of study epochs

Study Epochs	Blinding
Screening (Epoch 001)	N/A
1 st and 2 nd vaccination (Epoch 002)	observer-blind
Challenge (Epoch 003)	observer-blind

Sampling schedule:

- 5 mL for hematology: Screening Visit, Visit 2, Visit 3, Visit 4, Visit 5 and Visit 8. Additionally, hematology is repeated weekly until resolution if neutropenia occurs.
- 5 mL for biochemical analysis: Screening Visit.
- 10 mL for hepatitis B, hepatitis C and HIV: Screening Visit.
- 10 mL for HLA-B27 testing: Screening Visit.
- 5 mL for local anti S. sonnei LPS IgG Screening-ELISA: Screening Visit.
- Urine sample for urinalysis: Screening Visit and Visit 5.
- Urine sample for pregnancy test for women of childbearing potential: Screening Visit, Visit 1, Visit 3, Visit 5 and Visit 8.
- 20 mL for immunological tests (antibody response) at Visit 1, Visit 2, Visit 3,
 Visit 4, Visit 5, 7 days after Visit 5 (Day 64), Visit 6,
- For serum bactericidal activity tests at Visit 1, Visit 3 and Visit 5
- And for Fc glycosylation test on leftover serum samples collected at Visit 1 and Visit 5.
- 50 mL of peripheral venous blood for α4β7+/- plasmablast *analysis by ELISA* and RNA extraction from PBMCs for gene expression profiling: Visit 1, Visit 2, Visit 4 and 7 days after Visit 5 (Day 64). (Amended: 23 July 2019)
- Stool sample for inflammatory response before challenge at Visit 5 (Day 57) and daily, post challenge, during inpatient stay (Day 57 to Day 64).
- Stool sample: for microbiome testing at Visit 1 and Visit 5, for *S. sonnei* specific sIgA at Visit 1, Visit 2, Visit 4 and 7 days after challenge (Day 64) and stool analysis, culture and qPCR daily during inpatient stay (from Visit 5 to 7 days after challenge [Day 57 to Day 64] or prolonged until 2 consecutive negative stool samples if subject still shedding).

205626 (S SONNEI MONO GMMA SBVGH-003 [H03_03TP])
Protocol Amendment 6 Final

- Type of study: self-contained.
- **Data collection**: Standardized electronic Case Report Form (eCRF).
- **Safety monitoring:** An Independent Data Monitoring Committee (IDMC) will be established to monitor the safety of subjects throughout the study. The IDMC will review unblinded data, to assess safety signals and make recommendations to the Sponsor concerning continuation, termination, or other modifications of the study based on the observed adverse effects. The membership and roles of the IDMC will be outlined in the IDMC charter.

The safety review team (SRT) will monitor the safety of subjects throughout the study. The SRT will review blinded data, assess safety signals and make recommendations to the IDMC and Sponsor concerning continuation, termination, or other modifications of the study based on the observed adverse effects.

A dedicated Safety Management Plan will be prepared to ensure appropriate safety reporting responsibilities and roles are defined.

Refer to Section 9.10 for detailed description of holding rule and safety monitoring.

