4.2. Dysentery (Amended: 23 July 2019)

For the purpose of the endpoint "Rate of shigellosis as defined by the CHIM expert working group occurring within a period starting with challenge visit and lasting until the end of the inpatient stay, in all subjects", dysentery is defined as follows:

• At least 2 loose stools with gross blood (hemoccult positive) in 24 hours AND [oral temperature ≥38.0°C OR ≥1 moderate constitutional/enteric symptom OR ≥2 episodes of vomiting in 24 hours]. In this case constitutional/enteric symptom are the following: nausea, abdominal pain, abdominal cramping, myalgia, arthralgia, malaise.

For the purpose of the endpoint "Rate of shigellosis, as defined by: severe diarrhea OR moderate diarrhea with fever or with one or more moderate constitutional/enteric symptoms OR dysentery", dysentery is defined as follows:

• At least 2 loose stools with gross blood (hemoccult positive) in 24 hours AND [≥1 reportable constitutional/enteric symptom]. In this case constitutional/enteric symptom are the following: headache, fatigue, arthralgia, malaise, myalgia, chills, nausea, abdominal cramping, abdominal pain, gas, anorexia, vomiting.

For the purpose of the endpoint "Rate of more severe shigellosis as defined by: severe or moderate diarrhea with fever or with one or more severe constitutional/enteric symptom OR dysentery [[≥ 2 loose stools with gross blood (hemoccult positive) in 24 hours] AND [oral temperature $\geq 38.0^{\circ}C$ $OR \geq 1$ severe constitutional/enteric symptom]].", dysentery is defined as follows:

• At least 2 loose stools with gross blood (hemoccult positive) in 24 hours] AND [oral temperature ≥38.0°C OR ≥1 severe constitutional/enteric symptom]. In this case constitutional/enteric symptom are the following: headache, fatigue, arthralgia, malaise, myalgia, chills, nausea, abdominal cramping, abdominal pain, gas, anorexia, vomiting.

For the purpose of the endpoints "Dysentery" and "Confirmed S. sonnei 53G shedding AND moderate or severe diarrhea OR dysentery OR presence of oral temperature ≥ 38.5°C OR presence of one or more severe intestinal symptoms (abdominal pain, cramping, nausea, vomiting, gas, and anorexia)", dysentery is defined as follows:

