• A Grade 3, 4, or 5 stool with gross blood on at least 2 occasions within 24 hours and presence of constitutional/enteric symptoms. In this case, constitutional/enteric symptoms consist of headache, fatigue, arthralgia, malaise, myalgia, chills, nausea, abdominal cramping, abdominal pain, gas, anorexia, vomiting, and fever.

(Amended: 23 July 2019)

205626 (S SONNEI MONO GMMA SBVGH-003 [H03_03TP])
Protocol Amendment 6 Final

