4.3. Shigellosis

For the primary and secondary objectives in the challenge phase of the study, the protocol primary case definition for shigellosis is:

• Shedding of *S. sonnei* 53G accompanied by moderate or severe diarrhea OR shedding with an oral temperature of ≥ 38.5 °C).

For the secondary objectives in the challenge phase of the study, 2 definitions of shigellosis are used:

- 1. CHIM working group case definition for shigellosis as defined by any one of the three following possible endpoints:
 - Severe diarrhea defined as [≥6 loose stools in 24 hours] OR [>800 grams loose stools in 24 hours]
 - Moderate diarrhea defined as [4-5 loose stools in 24 hours OR 400-800 grams loose stools in 24 hours] AND [oral temperature ≥38.0°C OR ≥1 moderate constitutional/enteric symptom OR ≥2 episodes of vomiting in 24 hours]
 - Dysentery defined as [≥2 loose stools with gross blood (hemoccult positive) in 24 hours] AND [oral temperature ≥38.0°C OR ≥1 moderate constitutional/enteric symptom OR ≥2 episodes of vomiting in 24 hours].
- 2. Shigellosis as defined by any one of the three following possible endpoints:
 - Severe diarrhea defined as [≥6 loose stools in 24 hours OR >800 grams loose stools in 24 hours]
 - Moderate diarrhea defined as [4-5 loose stools in 24 hours OR 400-800 grams loose stools in 24 hours] AND [oral temperature ≥38.0°C OR ≥1 moderate constitutional/enteric symptom].
 - Dysentery defined as [≥2 loose stools with gross blood (hemoccult positive) in 24 hours] AND [≥1 reportable constitutional/enteric symptom].

For the secondary objectives in the challenge phase of the study, more severe shigellosis is defined by any one of the two following possible endpoints:

- Moderate OR severe diarrhea [≥4 loose stools in 24 hours OR ≥400 grams loose stools in 24 hours] AND [oral temperature ≥38.0°C OR ≥1 severe constitutional/enteric symptom].
- Dysentery defined as [≥2 loose stools with gross blood (hemoccult positive) in 24 hours] AND [oral temperature ≥38.0°C OR ≥1 severe constitutional/enteric symptom]. (Amended: 23 July 2019)

205626 (S SONNEI MONO GMMA SBVGH-003 [H03_03TP])
Protocol Amendment 6 Final

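### The cap of two Hemoccult tests per 24 hours equals the two positives that three secondary endpoints need, so one negative test can block their dysentery component; the practical loss is small

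*Protocol*

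**What the plan says.** Section 3.2 (Challenge Phase) describes stool handling during the inpatient stay. Loose or watery stools are weighed, and "if there is visible blood, a Hemoccult test will be performed to confirm presence of occult blood". The next sentence sets a ceiling: "Up to two stools with blood present by visual inspection in a 24 hour period will be tested by Hemoccult". That sentence is not restricted to loose stools. It does not provide for testing a further stool after a negative result, and it does not say whether the period is a calendar day or a rolling 24 hours.

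Section 4.2 sets the dysentery component of three secondary endpoints:
- CHIM shigellosis: "At least 2 loose stools with gross blood (hemoccult positive) in 24 hours AND [oral temperature ≥38.0°C OR ≥1 moderate constitutional/enteric symptom", or at least two vomiting episodes in 24 hours.
- Second shigellosis definition: "At least 2 loose stools with gross blood (hemoccult positive) in 24 hours AND [≥1 reportable constitutional/enteric symptom".
- More severe shigellosis: "At least 2 loose stools with gross blood (hemoccult positive) in 24 hours] AND [oral temperature ≥38.0°C OR ≥1 severe constitutional/enteric symptom".

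Section 4.3 repeats the requirement: "Dysentery defined as [≥2 loose stools with gross blood (hemoccult positive) in 24 hours".

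The stand-alone Dysentery endpoint and the composite built on confirmed shedding use another definition in Section 4.2, which has no Hemoccult condition: "A Grade 3, 4, or 5 stool with gross blood on at least 2 occasions within 24 hours and presence of constitutional/enteric symptoms".

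**The concern.** The largest number of tests allowed equals the smallest number of positives required. The rule therefore has no slack: a single negative result decides the matter for that testing period, and later bloody stools that could have supplied the second positive are not tested.

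At stake is complete ascertainment of one component in three secondary efficacy endpoints. One of these is the consensus CHIM definition. The other two were added in Amendment 5 so that results could be compared with other challenge studies. With 36 subjects planned per group, a few missed cases cost some precision.

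**Working it through.** **Counting check.** Tests allowed per period: 2 (Section 3.2). Positives needed: 2 (Sections 4.2 and 4.3). After one negative, the most that can be recorded is 2 − 1 = 1 positive, so the component fails for that period however many bloody stools follow. If a formed bloody stool takes one test, at most one loose stool can be confirmed, with the same result. With exactly two bloody loose stools and no formed bloody stool, the cap changes nothing.

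**Who actually loses case status.** Dysentery is only one route into each composite, so the other routes in Section 4.3 must be checked.

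| Endpoint | Diarrhea route | Symptom condition: diarrhea vs dysentery route |
|---|---|---|
| CHIM | 6 or more loose stools or >800 g outright; 4-5 stools or 400-800 g with symptom condition | Same: temperature ≥38.0°C, or a moderate symptom, or two vomiting episodes |
| Second definition | As CHIM | Different: diarrhea needs temperature ≥38.0°C or a moderate symptom; dysentery needs any one reportable symptom |
| More severe | 4 or more loose stools or ≥400 g with symptom condition | Same: temperature ≥38.0°C or a severe symptom |

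- CHIM and more severe shigellosis: anyone with at least 4 loose stools or 400 g who meets the dysentery symptom condition is already a case. What remains is essentially the subject with exactly 3 loose stools, all bloody, under 400 g, who does not qualify in another 24-hour window. If a formed bloody stool used up a test, two bloody loose stools are enough to be exposed.
- Second definition: the same subjects, plus those with 4-5 loose stools or 400-800 g whose symptoms are only mild and who have no temperature of 38.0°C or more.

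**Chance of confirmation.** The protocol gives no Hemoccult sensitivity, so take p as the assumed chance that a visibly bloody loose stool tests positive, independent between stools. For a subject with three such stools:
- under the cap: p²
- all tested: p³ + 3p²(1 − p)

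| p (assumed) | Cap | All three tested |
|---|---|---|
| 0.99 | 0.9801 | 0.9703 + 0.0294 = 0.9997 |
| 0.95 | 0.9025 | 0.8574 + 0.1354 = 0.9928 |
| 0.90 | 0.810 | 0.729 + 0.243 = 0.972 |
| 0.80 | 0.640 | 0.512 + 0.384 = 0.896 |

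With four bloody stools at p = 0.90 the contrast is 0.810 against 1 − 0.1⁴ − 4(0.9)(0.1³) = 0.9963, but by the table of routes this matters only for the second definition.

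Positive correlation between one subject's stools shrinks the gain. In the extreme where all of a subject's stools give the same result, the chance is p with or without the cap, and the gain is nil.

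**The case against.** Several points against the concern stand.

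- **The test only confirms.** It is run on stools that already show blood, so sensitivity may be high. At p = 0.99 the gap is about 2 percentage points, and only among the few exposed subjects.
- **The block is per period.** A subject may qualify on another day. If testing is counted by calendar day and the endpoint window rolls, a window across midnight could hold up to four tests. Against this, Section 3.2 counts gross blood in two or more stools among the symptoms that can lead to antibiotics before Day 62, and Section 1.3.1 expects these to reduce or eliminate symptoms within 24 hours. Some subjects may therefore have no second window.
- **The diarrhea routes catch most subjects**, as shown above. A reader might infer that everyone with 3-5 loose stools is exposed; for CHIM and more severe shigellosis that is not so.
- **The consequences are limited.** The primary case definition uses no Hemoccult result. Section 11.11 makes comparisons without a predefined success criterion descriptive.

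Two stronger readings are tempting. The first is that the estimate of vaccine efficacy is biased, because repeated bloody stools would be commoner on placebo. The documents do not support this: assessment is observer-blind (Section 6.3), the cap is the same in both arms, and missing the same fraction of cases in each arm leaves 1 − RR essentially unchanged. The second is that the cap makes the dysentery endpoints inconsistent with one another. They differ by design, since Section 4.2 sets separate definitions for separate endpoints, and lifting the cap would not align them.

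The general permission in Section 3.2 for additional investigations does not answer the point. It is left to the investigator's judgment, so testing beyond the cap could vary between subjects.

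**Conclusion.** The point holds as a minor defect of measurement. Followed exactly, Section 3.2 can leave a subject with three or more bloody loose stools unconfirmed after one negative test, and the dysentery component of three secondary endpoints is then blocked for that testing period. The harm is a few missed secondary cases and some lost precision. The primary endpoint, the stand-alone Dysentery endpoint and the confirmed-shedding composite are unaffected.

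The counting argument needs no outside figure. The percentages rest on an assumed sensitivity and on independence between stools, and they apply only to a subject with three bloody loose stools who has no other route to being a case. The protocol does not allow an estimate of how many of the 36 per group that would be.

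**What to change.** Replace the cap sentence in Section 3.2 with: *Each loose stool (grade 3-5) with visible blood is tested by Hemoccult until two positive results have been recorded within 24 hours.* State that the 24 hours are counted on the same basis as in the endpoint definitions.

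This keeps the two-positive requirement, stops a formed stool from using up a test, and leaves the workload unchanged when the first two loose stools tested are positive. The cost is one sentence and a few extra Hemoccult cards after a negative result. Testing on after a negative slightly raises the chance of a false-positive confirmation, but only visibly bloody stools are tested, so the increase is limited.
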